There were a total of 110 patients with ages ranging from 12 months to 60 years of age with median age being 11.4 years of age. Three dosage levels of VOR were utilized in these studies, 180 mg/m²/d, 230 mg/m²/d; and 300 mg/m²/d. These dosages were utilized as single agents or in combination therapy with 160 mg/m²/d of 14cRA; 150 mg/m²– 200 mg/m² TEM; 1.3 mg/m²/d BOR; 15 mg/m² DEC; or 8 - 18 mCi/kg MIBG.

Adverse events

As these were oncology studies, with the majority attempting to determine MTD, AEs were typically graded according to the National Institutes of Health Common Terminology Criteria for Adverse Events (CTCAE) (https://evs.nci.nih.gov/ftp1/CTCAE/CTCAE_4.03/Archive/CTCAE_4.0_2009-05-29_QuickReference_8.5x11.pdf).

Therefore the prevalence of reported AEs are presented utilizing this grading system. Briefly, Grade 1 refers to mild, asymptomatic; Grade 2 refers to moderate events, which may require non-invasive interventions; Grade 3 refers to events that are severe but not life-threatening; or required hospitalization or prolongation; Grade 4 refers to life-threatening events, and Grade 5 refers to events that lead to death.

The AE prevalence given below is for all patients in all reviewed studies evaluable for toxicity, at all doses of treatment for cycle 1 of treatment: (See Table 1 for all AEs reported)

- Across the five studies, there were a total of 378 AEs reported in 110 patients.
- Of the 378 AEs, 158 (42%) were rated as Grade 2; 145 (38%) as Grade 3; 72 (19%) as Grade 4; and 3 (0.8 %) were Grade 5.
- Grade 2-3 events: 45% of all Grade 2-3 AEs were hematologic type AEs; 27% were non-hematologic; less than 10% were laboratory abnormalities (see Table 1 for specific AEs); the most commonly reported Grade 2-3 AEs were **leukopenia** (38%); **lymphopenia** (23%); **thrombocytopenia** (17%); **neutropenia** (15%); and **anemia** (14%).
- Grade 4 events: 66% of all Grade 4 events were hematological; 26% were non-hematological; 7% were laboratory abnormalities (see Table 1 for specific AEs); the most commonly reported Grade 4 AEs were: **leukopenia** (32%); **lymphopenia** (26%); **thrombocytopenia** (22%); **nausea** (19%); **anemia** (18%); **neutropenia** (14%).
- Grade 5 events: there were 3 events that led to death: hemorrhage/bleeding event; hypoxia/acute respiratory distress, and CNS hemorrhage.

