A total of 17 studies were reviewed, however one study was the 12-month follow up of the original study, and another study was an analysis of the pediatric sub-population of the original study. The studies comprised of large multi-national studies within the last 25 years. The range of participants treated with VPA in these studies was 78 – 1192 in each study, for a total of 3,777 participants. Participants were followed between 4 weeks – 6.6 years. 3 studies included adult participants only; 9 studies included adult and pediatric participants, and 5 studies included pediatric patients only. 3 studies allowed for polytherapy. Patient populations included newly diagnosed patients; therapy-resistant patients; and those who attained remission but had relapsed. All studies with the exception of one were multi-centered. 12 studies were AED comparative studies, of these - 10 were randomized; 7 were double-blind; and 5 were open-label. 2 studies were dose concentration studies, where patients were randomized to a low or high concentration dose. 3

studies investigated various formulations of VPA only. Dosage ranged from 987 mg/day – 4114 mg/day for adult studies and combined adult/pediatric studies, and 17 mg/kg/day – 68.86 mg/kg/day for pediatric studies.

In general, most treatment emergent AEs considered related were generally rated as mild to moderate in severity; occurred early in therapy, were transient, and rarely required discontinuation; most SAEs were not considered related to study medication⁶⁶⁻⁶⁹. Rates of overall AEs with VPA ranged from 23% to 88% in the 6 studies that reported overall rates of AEs⁷⁰⁻⁷⁵ the other 11 studies did not report overall rates^{66-69, 76-81}. 13 studies reported 25 AE types that demonstrated a prevalence of $\geq 10\%$ ^{66, 69-74, 76, 77, 79-82}; 4 studies had no specific AE types that presented with a prevalence of $\geq 10\%$ ^{67, 68, 75, 78}.

Adverse Events

The most commonly reported AEs are shown in Table 2 below, only AEs with greater than $\geq 10\%$ prevalence within each study have been included.

TABLE 2: MOST COMMONLY REPORTED ADVERSE EVENTS (GREATER THAN 10% INCIDENCE) FOR VALPROIC ACID IN REVIEWED STUDIES (n=16)

| Reported Adverse Event | % of studies reporting AE (n/16) | Reported incidence rate |
|---------------------------|----------------------------------|-------------------------|
| Weight Gain | 56% (9/16) | 10-43% |
| Asthenia/Fatigue/Sedation | 44% (7/16) | 11-42% |

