TPM is also a 2nd generation AED, and like VPA is a broad-spectrum AED. In one study, the time to exit study for any reason did not differ between VPA, TPM, or CBZ⁶⁶. However in the pediatric substudy, discontinuation due to AEs was 32% for VPA, 14% for TPM, and 4% for CBZ⁷⁷. However in another study, which included an adult and pediatric population, there was no significant difference in overall clinically important AEs (22.7% VPA vs 24.9% TPM)⁷⁵. There was also no significant differences for treatment failure due to intolerable AEs⁷⁵.

LTG is also a 2nd generation AED. LTG has been suggested as an alternative to VPA, particularly for women of childbearing age, because of concerns about higher rates of teratogenicity and delayed cognitive development in children exposed to VPA in utero⁷³. However for time to treatment failure, there were significant differences between drugs, where VPA was the best option, as compared to LTG and TPM⁷³. Further, cumulative incidence analysis of treatment failure for intolerable AEs indicated that TPM is significantly inferior to both VPA and LTG⁷³. Similarly, another study also indicated that there was no significant difference in AEs leading to withdrawals between VPA and LTG⁷⁸. Another study compared VPA with LTG and ETX (another 1st generation AED). There were no significant differences among the treatment groups at 20 weeks in the frequency of treatment failures due to either intolerable AEs or withdrawal from the study⁸⁰. Although certain side-effects occurred more frequently among children treated with ETX or VPA, as opposed to LTG, these side effects were transient and did not require discontinuation of treatment⁸⁰. However by 12 months, the largest percentage of subjects discontinuing due to AEs were in the VPA group 9% vs 3% for LTG, and 1% for ETX⁸¹. Although VPA discontinuations were mostly due to weight increase after 20 weeks of therapy⁸¹. Another study also did not show statistical differences for treatment failure due to intolerable AEs between VPA, LTG and ETX⁶⁷

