5.2 OUTCOMES ASSESSMENTS

5.2.1 SAFETY AND TOLERABILITY ASSESSMENT

The safety and tolerability of VOR at a dose of 230 mg/m²/day in a pediatric population with medically intractable epilepsy will be assessed via incidence of AEs and SAEs, as well as discontinuations due to intolerable AEs, identified through Safety Monitoring Activities (See [Section 5.3](#)).

It is anticipated that the tolerability of VOR in a medically resistant population of pediatric patients with epilepsy will be similar to that seen with currently prescribed AED therapies. Namely, the incidence rate for overall AEs is anticipated to be up to 55%; incidence of SAEs to be no more than 10%; no deaths are expected in the course of the trial; and discontinuation rate due to intolerable AEs is expected to be up to 30%.

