7.2 HANDLING OF SAFETY PARAMETERS

7.2.1 REPORTING OF SERIOUS ADVERSE EVENTS

All new AEs occurring during the study should be recorded in the study record. AEs that occur intermittently will be recorded as a single AE. AEs will be collected and reported for up to 6 weeks after the last dose of study medication.

7.2.2 EXEMPTION OF PROJECT SPECIFIC SERIOUS AEs FROM IMMEDIATE REPORTING TO HEALTH AUTHORITIES AND IRBs

For any clinical AE or abnormal laboratory test value that is serious [as defined in Section 7.1.1.3], the investigator will complete SAE reporting in the study record within 24 hours of the study team becoming aware of the event. The REB and Health Canada will be notified as per reporting requirements.

SAEs monitoring and reporting will commence at the time following administration of the first dose of study medication until 6 weeks following administration of the last dose of study medication. At any time after the 6-week period following the last dose of study drug, only SAEs considered by the investigator to be related to study drug or protocol procedures will continue to be reported as stipulated.

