8.1 PRIMARY AND SECONDARY STUDY ENDPOINTS

8.1.1 PRIMARY ENDPOINTS

The primary endpoint for this study will be the incidence of related AEs and SAEs, and discontinuation of therapy due to intolerable AEs.

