8.2.2 ANALYSIS

8.2.2.1. SAFETY & TOLERABILITY ANALYSIS

Safety and tolerability will be assessed by calculating the incidence rate of AEs per number of drug days from the time medication is started through to the completion of the SFU (or 42 days following the last dose of study medication). This will be done for the following time points: 14 days following drug initiation; 30 days following drug initiation; 42 days following drug initiation; and 42 days following drug discontinuation. AEs will be further stratified by mild/moderate AEs, severe AEs, and SAEs, as well as project specific AEs (thromboembolism, hyperglycemia, gastrointestinal disturbances, dehydration, hematologic disturbances, QT/QTc prolongation).

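### The planned AE rate per drug-day generally cannot be set against the percentages expected in Section 5.2.1, and Section 8 contains no analysis of discontinuations

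*Combined protocol and SAP*

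**What the plan says.** All references are to the combined protocol and SAP.

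- **Endpoint (8.1.1).** "The primary endpoint for this study will be the incidence of related AEs and SAEs, and discontinuation of therapy due to intolerable AEs".
- **Analysis (8.2.2.1).** "Safety and tolerability will be assessed by calculating the incidence rate of AEs per number of drug days from the time medication is started", running to the safety follow-up visit or 42 days after the last dose. The time points are "14 days following drug initiation; 30 days following drug initiation; 42 days following drug initiation; and 42 days following drug discontinuation". Results are split into mild/moderate AEs, severe AEs, SAEs and project-specific AEs. The section plans no count or percentage of children and no confidence interval, and does not mention discontinuation.
- **Expectations (5.2.1).** "the incidence rate for overall AEs is anticipated to be up to 55" per cent, with SAEs at no more than 10% and discontinuation for intolerable AEs at up to 30%. No time window and no derivation are given beyond similarity to current AED therapies.
- **Recording rule (7.2.1).** "AEs that occur intermittently will be recorded as a single AE".
- **Background figures.** For the valproate review, Section 1.1.4.1 reports "Participants were followed between 4 weeks" and 6.6 years. The pediatric vorinostat AE figures in Section 1.1.3 are "at all doses of treatment for cycle 1 of treatment".
- **Analysis population (4.8).** Children who stop for non-safety reasons within 14 days of starting drug are left out of the final analysis.

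**The concern.** The trial's primary purpose is to characterize safety and tolerability, and Section 5.2.1 says in figures what is expected. A reader will want to put the result beside those figures. The planned statistic is on another scale: it counts events over exposure, whereas the expectations are percentages. One child with many events and many children with one event each give the same rate, yet they mean different things for tolerability.

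Two further gaps make this worse. Discontinuation is part of the primary endpoint but has no planned analysis. The rate that runs through follow-up puts events from the off-drug weeks over a denominator that, read literally, stops growing at the last dose. Section 3.2 says the findings may justify a larger randomized study, so the safety summary should be readable on the scale on which the expectations were set.

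**Working it through.** There is no power or precision figure to reproduce: Section 8.2.1 bases the sample size on feasibility and cost.

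**Inputs.** 12 children (3.3); 6 weeks = 42 days of drug, then 6 weeks of follow-up (3.1.2). With full treatment and follow-up, exposure is 12 × 42 = 504 drug-days and observation is 12 × 84 = 1,008 person-days. The AE counts below are illustrations, not forecasts.

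**1. Does the rate fix the percentage?** 12 AEs / 504 drug-days = 2.4 per 100 drug-days. The number of children affected can be anything from 1 (8%) to 12 (100%). The rate is informative only when counts are low, because affected children cannot outnumber event records:

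- At most 6 AEs (6/504 = 1.2 per 100 drug-days) means at most 6/12 = 50% of children, within 55%.
- 0 or 1 SAE means at most 1/12 = 8.3%, within 10%.

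The one-record rule in 7.2.1 does not close the gap. It merges recurrences of one AE, but a child with several different AEs still adds several records.

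**2. Denominator after the last dose.** Suppose 18 AEs are counted to 42 days after stopping. Over drug-days: 18/504 = 3.6 per 100. Over person-days: 18/1,008 = 1.8 per 100. If drug-days was meant as days since first dose, the second figure applies; the text does not say.

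**3. What 12 children can show.** Exact Clopper-Pearson 95% limits for x of n = 12 are the 2.5% point of Beta(x, n − x + 1) and the 97.5% point of Beta(x + 1, n − x). For x = 0 the upper limit is 1 − 0.025^(1/12) = 26.5%.

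| Children affected | Percentage | Exact 95% CI |
|---|---|---|
| 0/12 | 0% | 0 to 26.5% |
| 1/12 | 8.3% | 0.2 to 38.5% |
| 3/12 | 25% | 5.5 to 57.2% |
| 6/12 | 50% | 21.1 to 78.9% |

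The last three rows are the largest counts consistent with 10%, 30% and 55%. If the true rates were exactly 10%, 30% and 55%, the chance of falling at or below these counts would be 66%, 49% and 47% (binomial, n = 12).

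**4. Time window.** Section 5.2.1 does not say over what period its percentages accrue. Under a constant hazard (an assumption), a percentage p seen over T days becomes 1 − (1 − p)^(42/T) over 42 days. For p = 30%: T = 28 days gives 1 − 0.7^1.5 = 41%; T = 182 days gives 8%; T = 6.6 years (2,411 days) gives 0.6%. The adjustment can go either way, so without the source period its direction is unknown.

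**5. Units of one source.** Section 1.1.4.3 bases its view of discontinuation partly on the pediatric vorinostat studies, at 33%. Section 1.1.3 gives 36 AEs meeting dose-limiting criteria among 110 patients: 36/110 = 32.7%. By that count the figure is events per patient, although Section 1.1.4.3 describes it as a prevalence of patients.

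**The case against.** The fair defence is that this is a descriptive pilot. Section 5.2.1 speaks of what is anticipated, not of success criteria; no decision rule uses 55%, 10% or 30%; and Section 8.2.1 says the AE rate in this population is unknown. AEs are recorded for each child with onset, resolution and relationship (5.3.1), so percentages can be computed later. All of this stands. It places the defect in the planned summary, not in the data or design, but it does not make the planned rate answer the question that 5.2.1 poses.

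Three stronger readings are tempting, and the documents do not support them:

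- *The trial cannot show whether any expectation was met.* Very low counts do show it, and discontinuations are a simple count out of 12 that the drug-day scale does not affect. The fault there is that no analysis is written down.
- *All three percentages rest on follow-up of 4 weeks to 6.6 years.* That range describes the valproate review only. Section 5.2.1 refers to AED therapies generally, and the discontinuation expectation also draws on cycle-1 vorinostat data.
- *Any comparison favours vorinostat because its window is shorter.* Section 1.1.4.2 does report "Although VPA discontinuations were mostly due to weight increase after 20 weeks of therapy", but that is one study. Section 1.1.4.1 says most related valproate AEs came early, and its shortest follow-up is below 6 weeks. Step 4 shows that the direction can reverse.

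**Conclusion.** The point holds in a limited form. Except at very low counts (at most 6 AEs, or 0 to 1 SAE), the only AE and SAE statistic planned in 8.2.2.1 does not yield the percentages in which 5.2.1 is written. Discontinuation, part of the primary endpoint, has no analysis in Section 8. Read literally, the rate to 42 days after stopping mixes off-drug events with on-drug exposure, a factor of two between denominators under full treatment and follow-up.

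Even on the right scale, 12 children cannot confirm an SAE rate of 10% or less: with no SAE at all, rates up to 26.5% remain compatible with the data.

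The figures assume that all 12 children complete 42 days of drug and 84 days of observation. Early stopping changes the denominators but not the conclusion. Nothing here depends on the constant-hazard assumption, which serves only to show that the effect of the unstated window has no known direction.

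**What to change.** **Section 8.2.2.1.** Make the main statistics the number and percentage of all dosed children with:

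- at least one related AE (the endpoint in 8.1.1), and at least one AE of any cause (to match 5.2.1);
- at least one SAE, stating whether relationship to drug is required;
- discontinuation for an intolerable AE.

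Give each an exact Clopper-Pearson 95% interval. Report AEs and SAEs by day 42 and through 42 days after the last dose, and discontinuations by day 42. Keep event rates as supportive, with drug-days as the denominator on treatment and person-days once follow-up is included.

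**Section 4.8.** Reconcile the all-dosed safety denominator with the rule that drops early non-safety withdrawals from the final analysis.

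**Section 5.2.1.** Give the window and source for each expectation. Note that follow-up differs across sources (valproate review, 4 weeks to 6.6 years; pediatric vorinostat, cycle 1), so the direction of any period mismatch is unknown. State that 12 children cannot confirm an SAE rate of 10% or less.

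**Cost.** Some wording and one small table, with no new data. The intervals will be wide and will look less favourable than bare percentages or rates.

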3.1.2 PHASES OF STUDY

There are three phases to the study.

Phase 1: Screening period

During this phase, participants will be screened for study eligibility, which will last a total of 4 weeks. This will include several baseline investigations including full review of medical history and current medications, seizure frequency, physical examination, vital signs, laboratory safety testing, pregnancy testing for eligible patients, and electrocardiogram (ECG) (see Section 5 Schedule of Assessments and Procedures for complete list of screening procedures). In addition, baseline seizure frequency will be determined during this period. Clinically stable participants, fulfilling all eligibility criteria (see sections 4.2 and 4.3) will be enrolled in the treatment period of the study.

Phase 2: Treatment period

The duration of the treatment period will be 6 weeks. VOR will be given as fixed doses of 230 mg/m²/day. Following the enrollment visit, participants will visit the clinic for 2 more visits every 2 weeks, plus an end of treatment (EOT) visit (see Section 5.1 for detailed schedule). Participants may be seen more frequently for unscheduled visits for follow up of AEs, etc. as per the investigator's discretion. Study visits will include a physical examination, height and weight measurement, vital signs, pregnancy testing (required patients only). Safety monitoring during the treatment period will include laboratory safety testing and ECG. Investigators will review current medications, AEs, seizure diary/frequency at each visit. Investigators will assess study medication adherence at all visits; unused study medication will be returned to site at each visit and new study medication will be dispensed by local pharmacy, as recommended by the investigator. Unused study medication will be destroyed as per local standard operating procedures. All assessments and visit procedures will occur as stipulated in Section 5: Schedule of Assessments and Procedures.

Phase 3: Follow-up period

A safety follow-visit (SFU) will take place 6 weeks after the EOT Visit. The SFU visit will include a physical examination, height and weight measurement, vital signs. Safety monitoring for this visit will include laboratory safety testing and ECG. Investigators will review AEs since last visit and seizure diary/frequency. Any ongoing AEs will be followed by the investigator until resolution or stability.

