5.3 SAFETY MONITORING

5.3.1 ADVERSE EVENTS

AEs (serious and non-serious) reported by the participant or observed by the investigator will be collected throughout the study. At each visit, the investigator will ask the participant if any untoward medical event occurred since the last visit. For each event, the date of onset and date of resolution, intensity, relationship to study medication, outcome and treatments administered for the event will be recorded in the study record.

AEs will include any symptom, sign, illness or experience, or clinically relevant lab abnormality, regardless of causality, which develops or worsens in severity during the course of the study. An SAE will comprise of any AE, occurring at any dose, regardless of causality that was either life-threatening, requires inpatient hospitalization or prolonging an existing hospitalization, or is determined as an important medical event by the treating physician, or results in death.

All AEs will be reported as stipulated in [Section 7.1](#). SAEs will be reported to the research ethics board (REB) and to Health Canada.

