6.2.3 DOSE INTERRUPTIONS

If a dose is missed, it should be taken as soon as possible. If the participant does not remember until it is nearly time for the next dose, the participant should skip the missed dose and go back to the regular schedule. A double dose of should not be taken.

There will be no temporary interruptions of study medication due to safety reasons. If study medication is stopped due to safety reason, there will be no re-challenge.

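### Section 8.2.2.1 divides AEs by undefined drug days over a window that runs 42 days past the last dose, so its fourth time point has no sound rate; it also does not carry through the relatedness and discontinuation parts of the primary endpoint

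*Combined protocol and SAP*

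**What the plan says.** Section 8.2.2.1 sets the safety analysis as "calculating the incidence rate of AEs per number of drug days from the time medication is started through to the completion of the SFU", with 42 days after the last dose as the alternative end of the window. Rates are to be given at 14 and 30 days after initiation, and then at "42 days following drug initiation; and 42 days following drug discontinuation". AEs are split by severity, by seriousness and by the project-specific types.

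The follow-up matches that window. Section 3.1.2 gives six weeks of treatment, and then "A safety follow-visit (SFU) will take place 6 weeks after the EOT Visit". Section 7.2.1 adds that "AEs will be collected and reported for up to 6 weeks after the last dose of study medication".

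The primary endpoint in 8.1.1 is the "incidence of related AEs and SAEs, and discontinuation of therapy due to intolerable AEs". Section 5.2.1 names discontinuation as an outcome and adds that "discontinuation rate due to intolerable AEs is expected to be up to 30" percent. It also anticipates overall AEs in up to 55% and SAEs in no more than 10%.

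Section 5.3.1 provides the data needed: "For each event, the date of onset and date of resolution, intensity, relationship to study medication" are among the items recorded. Section 7.1.1.2 records relationship as Yes or No.

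**The concern.** The numerator runs to six weeks after dosing ends, while the denominator is named as drug days and not defined. Four readings are possible:

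- **First to last dose, fourth time point cumulative.** Off-drug events are set over on-drug time.
- **First to last dose, fourth time point as its own interval.** There are no drug days in that interval, so no rate exists.
- **All days to the SFU.** Exposed and unexposed time are merged into one rate.
- **Days actually dosed.** Missed doses shrink the denominator, since under 6.2.3 a participant who remembers late is told that "the participant should skip the missed dose and go back to the regular schedule".

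Safety and tolerability are the primary objective, and the study has no control arm. If the choice is made after the data are in, a reader cannot tell what the reported rate measures. In addition, the analysis section does not summarise what 8.1.1 defines: it analyses all AEs rather than related ones, and says nothing about how discontinuation will be reported.

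**Working it through.** The documents give no AE rate per drug day, so there is no stated figure to reproduce. The check is person-time arithmetic.

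**Inputs.** Treatment 42 days and follow-up 42 days (3.1.2), so 84 days for a completer; compliance threshold 80% (6.3); 12 participants (3.3).

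**1. Fourth time point, cumulative, completer.** With the AE count held fixed, the rate is inversely proportional to the denominator. As an example, take 7 AEs (assumed) in 12 completers:

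| Reading of drug days | Days per completer | Ratio to all-days rate | 7 AEs, per 100 days |
|---|---|---|---|
| All days to SFU | 84 | 84/84 = 1 | 7/1008 = 0.69 |
| First to last dose | 42 | 84/42 = 2.0 | 7/504 = 1.39 |
| Days dosed, at exactly 80% | 0.8 × 42 = 33.6 | 84/33.6 = 2.5 | 7/403.2 = 1.74 |

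With the visit windows of Table 5 (EOT day 40 to 44, SFU day 79 to 89), the factor 2.0 ranges from 79/44 = 1.8 to 89/40 = 2.2. Read as a separate interval, the fourth time point has 0 drug days and the rate is undefined.

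**2. Days 14, 30 and 42.** For a participant still on drug, all days and first to last dose coincide. Only the days-dosed reading differs, by at most 1/0.8 = 1.25 at 80% compliance or better. An early stopper is different: someone who stops at day 14 contributes 42 days of events over 14 drug days at the day-42 time point (42/14 = 3.0), and 56/14 = 4.0 at the fourth.

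**3. Distance from the on-drug rate at the fourth time point.** Let r be the off-drug AE rate divided by the on-drug rate. The documents do not give r; the assumed range is 0, 0.5, 1.

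- First to last dose, all complete: 1 + r = 1.0, 1.5, 2.0.
- All days, all complete: (1 + r)/2 = 0.5, 0.75, 1.0.
- First to last dose with early stopping. Assume 4 of 12 stop for safety at day 14 and everyone is followed for 42 days off drug. Drug days are 8 × 42 + 4 × 14 = 392, and off-drug days are 12 × 42 = 504. The ratio is 1 + r × 504/392 = 1.00, 1.64, 2.29.

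So the first-to-last-dose reading is undistorted only when r = 0, and the all-days reading only when r = 1.

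**4. Endpoint against analysis.**

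| Component in 8.1.1 | In 8.2.2.1 |
|---|---|
| Related AEs | All AEs; relatedness is not a stratum |
| SAEs | Present as a stratum, not split by relatedness |
| Discontinuation for intolerable AEs | No summary given |

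**The case against.** The strongest reply is that the ordinary meaning of drug days is first to last dose, and the context supports it. Section 6.2.3 rules out temporary safety interruptions and re-challenge, so dosing is one continuous run apart from missed doses. Section 4.7 sets a last assumed medication day for participants lost to follow-up. On that view the all-days reading is strained, the usable readings differ by no more than 1.25, and the planned day-42 rate is already close to an on-treatment rate for completers. This is largely right about the size. It does not rescue the fourth time point, where first to last dose still gives either off-drug events over on-drug days or a zero denominator. Nor does it deal with early stoppers at the earlier time points.

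The reply also holds that discontinuation is a named endpoint, for which a simple proportion is the evident summary, and that relatedness is both named and collected. That is fair: the gap is that 8.2.2.1 does not carry them through.

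Three stronger inferences are tempting and are not supported:

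- **That the main AE rate is uncertain by 2.0 to 2.5 throughout.** Nothing makes the fourth time point the headline rate. The factor needs the all-days reading, and its upper end needs compliance of exactly 80%, which 6.3 gives as a definition and not as an expectation.
- **That early stopping necessarily inflates the rate.** It does so only if AEs also occur off drug; at r = 0 the ratio stays at 1.00.
- **That the 55%, 10% and 30% are thresholds that a per-day rate fails to test.** Section 5.2.1 gives them as expectations, and no decision rests on them.

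**Conclusion.** The concern holds in a limited form. At the fourth time point no reading of drug days gives a sound rate. The all-days and first-to-last-dose readings differ there by 2.0 for a completer, and by 2.5 if days dosed at exactly 80% compliance are used. This spread follows from the 42-day and 84-day schedule and needs no assumption about risk. Any statement about bias against the true on-drug rate does need one: under first to last dose the rate is inflated, and rises with early stopping, only if r > 0. At days 14, 30 and 42 the spread is at most 1.25 for participants still on drug at 80% compliance or better, although early stoppers bring off-drug events into those time points too.

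The mismatch between 8.1.1 and 8.2.2.1 is independent of the denominator and is the firmer half of the point: relatedness and discontinuation are primary-endpoint components without a specified summary. Both halves should be settled before the data are analysed.

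**What to change.** In 8.2.2.1:

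- **(a)** Define drug days as first to last dose inclusive, without subtracting skipped doses (compliance can be reported separately). State that the day 14, 30 and 42 time points are cumulative.
- **(b)** Classify AEs by onset date and report two rates: on-treatment AEs over drug days, and post-treatment AEs over observed post-treatment days, up to 42. Show each for all AEs and for related AEs. Do not divide post-treatment events by drug days.
- **(c)** Add the number and proportion of participants with at least one AE, at least one related AE, at least one SAE (all and related), and discontinuation due to an intolerable AE, each with an exact (Clopper-Pearson) 95% CI. Present these descriptively, with no test. They are on the same scale as the expectations in 5.2.1, which remain expectations and not criteria.

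The cost is a few sentences and some table rows. Onset date and relationship are recorded under 5.3.1, and the reason for stopping under 4.7 and 7.1.3. There are two downsides. Intervals are wide at n = 12: 4/12 = 33.3% has limits 9.9% to 65.1%, and 1/12 = 8.3% has 0.2% to 38.5%. A strict cut at the last dose also places delayed drug reactions in the post-treatment rate, where the related-AE row keeps them visible.
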